Ganoderma lucidum is a species from *Ganodermataceae* family that has Beta-1,3/1,6-D-Glucan as one of active compound from isolated mycelium extract *Ganoderma lucidum*. This compound has biologic effect as immunomodulator and has been used to prevent and treat diseases such as gastric ulcer, arthritis, atherosclerosis, asthma, diabetes, cancer and other diseases related to immune disorders.^{10,11} A study on patient with CD showed that *Ganoderma lucidum* decrease TNF- α , IFN- γ , IL-17A from inflammation of intestinal mucosa.⁹ On the other hand, there is no study about the role of Beta-1,3/1,6-D-Glucan *Ganoderma lucidum* in UC.

Objective

General objective

To know the role of Beta-1,3/1,6-D-Glucan from mycelium extract of *Ganoderma lucidum* administration in ulcerative colitis

Specific objectives

1. To know the quality of life from patient with ulcerative colitis after Beta-1,3/1,6-D-Glucan mycelium extract of *Ganoderma lucidum* administration
2. To know the level of inflammatory marker from patient with ulcerative colitis after Beta-1,3/1,6-D-Glucan mycelium extract of *Ganoderma lucidum* administration
3. To know the Mayo score from patient with ulcerative colitis after Beta-1,3/1,6-D-Glucan mycelium extract of *Ganoderma lucidum* administration

Methods

Study Design

This research is a double blind, randomized clinical trial method. Analysis will be conducted pre and post administration: control (placebo) and intervention (polysaccharide peptide *Ganoderma lucidum*) 3 times daily for 90 days.

Location and Time

This research will be conducted on Indonesia from August 2019 to December 2020

Population and Subject

Population

The population of this research is patients diagnosed with ulcerative colitis in Indonesia

Subjects Criteria

- Inclusion criteria

1. Subjects aged ≥ 18 years old
2. Ulcerative colitis patients who are treated by 5-ASA 3x500 mg
3. Agreed to participate

- Exclusion criteria

1. Allergic with *Ganoderma lucidum*

2. Ulcerative colitis patients who are treated by corticosteroid, immunosuppressive agent, biologic agent
3. Could not be randomised and participate in this study by clinical judgement

Drop Out Criteria

Drop out subjects are subjects who have signed the informed consent but decide to withdraw before research is completed

Estimated Sample Size

Minimum sample size is determined using the following equation for proportion equation.

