$$N1 = N2 = \frac{(Z_{\alpha}\sqrt{2PQ} + Z_{\beta}\sqrt{P_1Q_1 + P_2Q_2})^2}{(P_1 - P_2)^2}$$

Description :

$$Z_{\alpha} = 1.96 \quad Z_{\beta} = 0.84$$

$$P_1 - P_2 = 0.2 \quad P_1 = 0.554^{12}$$

$N1 = N2 = 92.25$, thus with predicted drop out 10% the minimal sample for each group is 102 subjects

Randomization

Randomization is generated by computer and subjects will be given code and divided into two groups (control and intervention). Researcher and subjects are blinded to treatment.

Variables

Independent Variables

1. Intervention: administration of capsule contain Beta-1,3/1,6-D-Glucan as active form of polysaccharide peptide from mycelium extract *Ganoderma lucidum* 3 times daily
2. Control (placebo): administration of empty capsule 3 times daily

Dependent Variables

1. Quality of life; assessed by Indonesian validated SF-36 questionnaire
2. Erythrocyte Sedimentation Rate (ESR), C-Reactive Protein (CRP), Tumor Necrosis Factor Alpha (TNF- α) and Interleukin 6 (IL-6) from blood samples

3. Fecal calprotectin from stool examination
4. Mayo Score from colonoscopy
5. Biopsy

Procedure

1. Eligibility assessment

The subjects will be assessed for eligibility using inclusion and exclusion criteria.

2. Subjects sign the informed consent form
3. Randomization
4. Pre-administration

Before administration of polysaccharide peptide or placebo based on randomization, subjects will be analysed for his/her quality of life by SF 36 questionnaire, ESR, CRP, TNF- α , IL-6, fecal calprotectin, colonoscopy (Mayo Score) and biopsy.

5. Administration (90 days)

Subjects will be given *Ganoderma lucidum* and placebo that will be taken three times daily for 90 days. The drugs are given monthly to the subjects.

6. Compliance monitoring

Compliance monitoring of administration is conducted by the investigators coordinating with his/her family and checked monthly when the patients came to take the capsule for the next month

7. Post administration

[figure not shown]
After 90 days the subjects will be analysed for his/her quality of life by SF 36 questionnaire, ESR, CRP, TNF- α , IL-6, fecal calprotectin, colonoscopy (Mayo Score) and biopsy.

8. Data analysis

- a. Normality analysis using Kolmogorov-Smirnov (Normally distributed if $p > 0.05$)
- b. Bivariate analysis by comparing numeric data between two groups: if data is normality distributed using T-test, if not using Mann-Whitney test (significant if $p < 0.05$)

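### Treatment changes during the 90 days need not be recorded, and the pre/post tests can credit rescue, placebo response or drift to the capsule

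*Combined protocol and SAP*

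**What the plan says.** Two entry criteria fix background therapy. Inclusion 2 admits "Ulcerative colitis patients who are treated by 5-ASA 3x500 mg". Exclusion 2 removes "Ulcerative colitis patients who are treated by corticosteroid, immunosuppressive agent, biologic agent". Procedure step 1 applies them: "The subjects will be assessed for eligibility using inclusion and exclusion criteria". That step comes before consent and randomization.

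During the 90 days, step 5 covers supply of the capsule ("The drugs are given monthly to the subjects") and step 6 covers compliance with it, checked at the same monthly contact. Neither mentions other colitis treatment. The drop-out definition reads "Drop out subjects are subjects who have signed the informed consent but decide to withdraw before research is completed", so it depends on the subject's own decision. Step 7 then measures every outcome: "After 90 days the subjects will be analysed for his/her quality of life by SF 36 questionnaire, ESR, CRP, TNF" and the remaining markers, colonoscopy and biopsy.

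Data analysis b and c compare the two groups. Items d and e compare values before and after administration, each with significance at p < 0.05. No analysis set and no rule for rescued patients is given. The specific objectives are worded as the patient's state following the capsule, for example "To know the Mayo score from patient with ulcerative colitis after Beta-1,3/1,6-D-Glucan mycelium extract of" the mushroom.

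**The concern.** The drugs barred at entry act on the outcomes being measured. Suppose a patient flares in week 5, starts a corticosteroid and stays in the trial. That patient is not a drop-out under the definition given, and nothing asks for the steroid to be written down. Two consequences follow.

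First, if escalation is more frequent in the arm doing worse, the between-group difference shrinks. A small difference could then mean an ineffective capsule or more rescue on placebo. Without dated starts by arm, the required data could not tell these apart, and analysts cannot recover what was never collected.

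Second, a pre/post comparison has no control. Rescue, placebo response and regression to the mean all count as improvement after the capsule, and objectives worded as the state after administration invite that reading.

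**Working it through.** **Inputs.** The documents give no rescue rate, no size of gain after rescue, and no requirement of active disease at entry. All rates and gains below are assumptions, and the plausible range starts at zero.

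The arm size of 92 comes from the plan's 92.25 per group. The printed formula gives 95.99 (second proportion 0.354) or 87.52 (0.754). The unpooled form, (1.96 + 0.84)² × (0.554 × 0.446 + 0.354 × 0.646) / 0.2² = 93.25, is within about one patient of 92.25. Then 92.25 × 1.1 = 101.5, rounded up to the stated 102. Nothing below depends on which form was used.

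**Check 1: between-group comparison, rescue following the disease.** Control values are N(0,1) and active values N(−0.415,1), higher being worse. The difference of 0.415 SD gives t-test power 0.80 at 92 per arm. Patients above one common threshold c are escalated and improve by g SD. If a share f0 of control exceeds c, the active share is f1 = 1 − Φ(c + 0.415), and the expected difference is 0.415 − g(f0 − f1). For f0 = 10%: c = 1.282, f1 = 4.5%, and 0.415 − 1 × (0.100 − 0.045) = 0.360. Power is from 10,000 simulated trials.

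| Escalated, control v active | Difference, g = 1 | Power | Difference, g = 2 | Power |
|---|---|---|---|---|
| none | 0.415 | 0.80 | 0.415 | 0.80 |
| 5% v 2% | 0.385 | 0.79 | 0.354 | 0.75 |
| 10% v 4.5% | 0.360 | 0.79 | 0.305 | 0.68 |
| 20% v 10% | 0.319 | 0.75 | 0.224 | 0.50 |

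At a 1 SD gain the estimate falls by 7% to 23% and power changes little. Material loss of power needs the 2 SD gain.

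**Check 2: equal starts.** With 5% or 10% escalated in each arm, the difference stays at 0.415. At a 1 SD gain, t-test power is about 0.86 or 0.90 if the worst patients are escalated, and about 0.78 or 0.77 if starts are unrelated to outcome.

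**Check 3: no true effect.** With the same rescue rule in both arms, the observed values have the same distribution in each, so the size of the test is kept. Repeated simulation at a 2 SD gain gave upper-tail rejection of 0.022 to 0.027 against a nominal 0.025, with simulation error of about ±0.003.

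**Check 4: pre/post test in one arm, no capsule effect.** This is a different model from check 1: SDs are of the change score, and rescue is unrelated to outcome. The mean change is drift + f·g, the variance is 1 + f(1 − f)g², and the paired t-test has n = 92. For f = 0.10, g = 1, no drift: 0.10 / √1.09 × √92 = 0.92 as non-centrality, giving probability 0.147. For drift 0.2 and no rescue: 0.2 × √92 = 1.92, giving 0.475.

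| Drift (SD) | Gain (SD) | 0% rescued | 5% | 10% | 20% |
|---|---|---|---|---|---|
| 0 | 1 | 0.025 | 0.07 | 0.15 | 0.42 |
| 0.1 | 1 | 0.16 | 0.29 | 0.44 | 0.75 |
| 0.2 | 1 | 0.48 | 0.64 | 0.78 | 0.94 |
| 0 | 0.5 | 0.025 | 0.04 | 0.07 | 0.15 |

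The values depend on the model. If instead the worst patients are rescued and the gain is 1 SD of the outcome, 20% rescue with no drift gives roughly 0.4 to 0.7 as the pre/post correlation runs from 0.3 to 0.7, against 0.42 in the table.

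**The case against.** The case for leaving the plan alone is substantial. Comparing observed values whatever else was taken is a legitimate treatment-policy choice. Entry does not require active disease, so rescue may be rare and its effect negligible. The most damaging between-group figures need 10% to 20% of controls escalated with a 2 SD gain, and no document supports either. Sites may hold medication changes in clinical records, and the flow chart, which might show a withdrawal rule, was not available. All of this stands, and it is why the point is a low-cost improvement and not a flaw in the main comparison.

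A reader might infer that the between-group test is biased towards a false claim. The documents do not support that: the plan states "Researcher and subjects are blinded to treatment", and checks 2 and 3 show no inflation and no shrinkage when starts are equal. A reader might also infer that the plan keeps rescued patients in the analysis. It does not say so; inclusion without a mark is only the default reading of its silence.

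One part of the objection fails. That rescue may be rare is not a reason to leave it unrecorded: the record would show it was rare, at almost no cost.

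**Conclusion.** The point holds as an omission with two modest consequences. On-study escalation is not required to be recorded, so any shrinkage of the between-group difference could not be examined. That comparison itself remains valid. The pre/post tests at p < 0.05 cannot support conclusions about the capsule: under the stated assumptions (92 per arm, SDs of the change, rescue unrelated to outcome), a null capsule shows significant improvement with probability about 0.15 at 10% rescue with a 1 SD gain, or 0.48 with 0.2 SD drift alone, against 0.025. Other assumptions give other values.

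It would be too strong to say that rescue is what undermines the pre/post tests, or that counting it would repair them. Drift alone can do as much. Severity: low-cost improvement, resting on the available text without the opening page and flow chart.

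**What to change.** 1. At each existing monthly capsule visit and at Day 90, record with date and reason any start of a corticosteroid, immunosuppressant or biologic and any change of 5-ASA from 3x500 mg. Report counts by arm. Whether to give other treatment stays with the treating doctor.
2. State before unblinding that conclusions about the capsule rest on the between-group comparison of observed values, and label Data analysis d and e as descriptive, whatever the rescue counts show.

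Optional: a pre-specified sensitivity analysis giving patients escalated for worsening colitis the worst rank in a Mann-Whitney test, or counting them as failures in any responder comparison the sponsor defines. It should not be primary. When the worst 5% to 10% of each arm are escalated, worst-rank power is about 0.74 to 0.77 against 0.86 to 0.90 for the t-test. When 5% or 10% are escalated at random, it is about 0.69 or 0.60.

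Cost: one more line per existing visit and a few sentences in Data analysis, with no extra visit or procedure. The downside is that within-arm p-values would no longer support efficacy claims.

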- c. Bivariate analysis by comparing categorical data between two groups: if data is normality distributed using T-test, if not using Mann-Whitney test (significant if $p < 0.05$)

- d. Bivariate analysis by comparing numeric data between preadministration and postadministration: if data is normality distributed using paired T-test, if not using Wilcoxon test (significant if $p < 0.05$)
- e. Bivariate analysis by comparing categorical data between preadministration and postadministration: if data is normality distributed using Mc Nemar test, if not using Wilcoxon test (significant if $p < 0.05$)

Study flow chart

Ethical committee approval

Approval from the Ethical Committee at the Faculty of Medicine Universitas Indonesia must be obtained before starting the trial.

References

7. Ng SC. Epidemiology of Inflammatory Bowel Disease: Focus on Asia. *Best Pract Res Clin Gastroenterol.* 2014.

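### A Kolmogorov-Smirnov pre-test picks the test for every numeric outcome, and the plan has no baseline-adjusted model on a suitable scale, no effect estimate and no confidence interval

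*Combined protocol and SAP*

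**What the plan says.** In the combined protocol and SAP, Procedure, step 8 (Data analysis):

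- Item a: "Normality analysis using Kolmogorov-Smirnov (Normally distributed if" p > 0.05). The text does not say whether the test is run per arm or pooled, on values or on changes, or with a correction for estimated mean and SD.
- Item b, between groups: "comparing numeric data between two groups: if data is normality distributed using T-test, if not using Mann-Whitney test". It does not say whether Day-90 values or changes are compared.
- Item d, before against after: "if data is normality distributed using paired T-test, if not using Wilcoxon test". It does not say whether normality is judged on the measurements or on the within-subject differences.

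Items b and d each end in a 0.05 significance threshold. Neither branch names an effect measure, a confidence interval, a transformation or a covariate.

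Dependent Variables, item 2, lists "Erythrocyte Sedimentation Rate (ESR), C-Reactive Protein (CRP"), TNF-alpha and IL-6, and item 3 adds fecal calprotectin. Steps 4 and 7 of the Procedure measure all five before treatment and after 90 days. Items c and e, on categorical data, are outside this point.

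**The concern.** Specific objective 2 asks about the level of inflammatory markers after treatment. A p-value alone does not say by how much a marker fell, and this gap exists in both the T-test and the rank-test branch.

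Baseline values are collected but enter no between-group analysis named in the plan. Where baseline predicts the Day-90 value, ignoring it wastes power. Using it through raw subtraction can also waste power if the marker is right-skewed, because raw changes are then dominated by the few subjects with high baselines.

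The test reported for a given marker would also depend on a preliminary result from the trial's own data, and on which version of the Kolmogorov-Smirnov test the software runs.

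**Working it through.** **Inputs from the documents.** Two-sided alpha 0.05 (z 1.96), power 80% (z 0.84), P1 = 0.554, difference 0.2, stated N of 92.25 per group before dropout.

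**The plan's own figure.** With P2 = 0.354, mean P = 0.454 and Q = 0.546, the printed formula gives:

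- 1.96 × √(2 × 0.454 × 0.546) = 1.96 × 0.7041 = 1.3801
- 0.84 × √(0.554 × 0.446 + 0.354 × 0.646) = 0.84 × 0.6898 = 0.5794
- (1.3801 + 0.5794)² / 0.2² = 3.8396 / 0.04 = 95.99

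With P2 = 0.754 it gives 87.52. Neither is 92.25; an unpooled-variance variant with P2 = 0.354 comes nearest, at 93.25. That is a separate query to the sponsor. This point uses 92 per arm as the plan's evaluable number and does not depend on the mismatch.

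**Assumptions (not in the documents).** Markers are lognormal with log-SD 0.8, 1.0 or 1.2. The baseline to Day-90 log correlation is 0.4 or 0.6. The true shift is 0.415 log-SD, set so that a log T-test on Day-90 values has about 80% power. That shift means ratios of exp(−0.415 × 0.8) = 0.72, exp(−0.415) = 0.66 and exp(−0.415 × 1.2) = 0.61.

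**Closed-form check.** Standard error in log-SD units: √(2/92) = 0.1474. Power ≈ Φ(shift / (SE × k) − 1.96), where k scales the SD.

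- Log T-test, Day 90 only (k = 1): Φ(2.815 − 1.96) = 80%
- Mann-Whitney, Day 90 only (efficiency 0.955, so k = 1/√0.955): Φ(2.75 − 1.96) = 79%
- Log ANCOVA, k = √(1 − r²): r = 0.4 gives Φ(3.07 − 1.96) = 87%; r = 0.6 gives Φ(3.52 − 1.96) = 94%
- T-test on log change, k = √(2(1 − r)): r = 0.4 gives Φ(2.57 − 1.96) = 73%; r = 0.6 gives Φ(3.15 − 1.96) = 88%

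**Simulated power, 92 per arm, 3,000 replicates, range over log-SD 0.8 to 1.2.**

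| Analysis | r = 0.4 | r = 0.6 |
|---|---|---|
| Mann-Whitney on raw change | 56-59% | 71-76% |
| T-test on log change | 71-73% | 87-88% |
| ANCOVA, raw scale | 56-71% | 63-81% |
| ANCOVA, log scale | 86-87% | 93-94% |

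On Day-90 values alone, Mann-Whitney has 76-79% and the log T-test 79-81%. Over repeat runs the full ranges are 54-77% for Mann-Whitney on raw change, 56-82% for raw ANCOVA and 85-95% for log ANCOVA.

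**Separating the causes.**

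- *Pre-test.* In 10,000 trials per scenario (log-SD 0.3 to 1.25), the two-stage rule on Day-90 values was 1.4 to 2.4 points below a log T-test and within about 0.5 point of always using Mann-Whitney. Its type I error was 4.7-5.3%.
- *Baseline.* The same two-stage rule was 5-6 points below log ANCOVA at correlation 0.3, 11-12 at 0.5 and about 19 at 0.7.
- *Scale.* Ranks of Day-90 values are the same raw or logged, but ranks of changes are not. At r = 0.6, Mann-Whitney on log change has 86% power, against 70-75% on raw change. At log-SD 1.2, raw ANCOVA has 63%, below the 77% of unadjusted Mann-Whitney on Day-90 values.

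**Stability of the pre-test.** Share of single lognormal samples of 92 called normal, plain against corrected Kolmogorov-Smirnov: 84% against 21% at log-SD 0.4; 65% against 7% at 0.5; 42% against 3% at 0.6. If both arms must pass at log-SD 0.5, the plain version passes about 0.65² = 42% of trials (about 40% in simulation). At log-SD 0.75 or more, about 99-100% of Day-90 comparisons go to Mann-Whitney.

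**The case against.** The strongest defence is that the pre-test does little harm and some good. For clearly skewed Day-90 values it leads to Mann-Whitney, a valid and robust test. At log-SD 1.25 the two-stage rule has 78.7% power against 51.9% for an unconditional raw T-test. Its instability at moderate skew barely moves power: 78.9% with the plain version and 80.0% with the corrected one at log-SD 0.4, and 77.9% against 78.3% at 0.6. This stands. A reader might infer that the pre-test is what costs power, or that it inflates false positives; neither is supported.

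Other inferences also go too far:

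- *That item b compares raw changes.* It does not say so. On the Day-90 reading the shortfall against log ANCOVA is smaller, though still material.
- *That the rank tests cause the missing effect size.* No estimate is promised in either branch, and a rank test can carry a Hodges-Lehmann shift in marker units.
- *That item d tests the wrong quantity.* The wording may mean the differences. It is ambiguous, not shown to be wrong.
- *That the documents show skewed markers.* They give no SD, distribution, correlation or effect for any marker. Lognormality with a proportional effect favours the log model, and the simulation has no values at a detection limit.

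It can also be said that baseline adjustment, not the logarithm, brings most of the gain. A rank-based ANCOVA reached 91.1-92.6% at correlation 0.6, against 93.1-94.5% for log ANCOVA. That stands too: ranks are a suitable scale for power, but they give no ratio estimate. It does not rescue adjustment on the raw scale.

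**Conclusion.** The concern holds as a recommended improvement, not as a threat to validity. The plan lets a pre-test choose the test for all numeric outcomes and specifies no baseline-adjusted model, effect estimate or confidence interval. The pre-test accounts for about 2 points of power. The main shortfall is from not using baseline on a suitable scale: about 76-79% (Day-90 values) or 54-77% (raw changes), against about 85-95% for log-scale ANCOVA. These figures rest on lognormal markers with log-SD 0.8 to 1.2, correlation 0.4 to 0.6, 92 per arm and a shift of 0.415 log-SD, all assumed except the arm size. The direction is the same under either reading of item b. The missing estimate and interval are plain from the text and need no assumption.

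**What to change.** Remove item a as a decision rule. Then:

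- **Item b, markers.** Analyse Day-90 ESR, CRP, TNF-alpha, IL-6 and fecal calprotectin on the natural-log scale by ANCOVA with log baseline as covariate. Report the ratio of geometric means (intervention/placebo) with 95% CI. State a fixed rule for values below the detection limit, for example half the limit.
- **Item b, SF-36.** Analyse scores by ANCOVA on baseline and report the mean difference with 95% CI, without a normality gate.
- **Sensitivity.** Keep Mann-Whitney as a prespecified sensitivity analysis, stating which values it compares.
- **Item d.** Drop the gate and report within-subject differences (log differences for the markers) descriptively.

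The cost is SAP wording only: both measurements are already scheduled, and no patients or samples are added. The downsides are that a detection-limit rule must be fixed in advance and that the log model assumes roughly proportional effects, which the Mann-Whitney sensitivity analysis helps to check.

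### The between-arm test for numeric outcomes leaves the compared quantity undefined and makes no baseline adjustment, while the pre/post tests carry the same significance rule

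*Combined protocol and SAP*

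**What the plan says.** Procedure step 8 (Data analysis) lists five items.

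- **Item b**, between arms, numeric data: "Bivariate analysis by comparing numeric data between two groups: if data is normality distributed using T-test, if not using Mann-Whitney test". No time point, change score or covariate is named.
- **Item d**, pre against post, numeric data: "Bivariate analysis by comparing numeric data between preadministration and postadministration: if data is normality distributed using paired T-test, if not using Wilcoxon test".
- **Item e**, pre against post, categorical data: "Bivariate analysis by comparing categorical data between preadministration and postadministration: if data is normality distributed using Mc Nemar test, if not using Wilcoxon test".

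Items b to e all use the 0.05 threshold. No item is ranked above another, no primary analysis is named, and no regression or other baseline adjustment appears.

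Study Design says: "Analysis will be conducted pre and post administration: control (placebo) and intervention". Procedure steps 4 and 7 collect the same outcomes at both visits: "Before administration of polysaccharide peptide or placebo based on randomization, subjects will be analysed for his/her quality of life by SF 36 questionnaire", and "After 90 days the subjects will be analysed for his/her quality of life by SF 36 questionnaire". In each case ESR, CRP, TNF-alpha, IL-6, fecal calprotectin and the Mayo score follow in the same sentence. The baseline values needed for an adjusted analysis will therefore be available.

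**The concern.** Two things are left open.

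First, item b can be run on day-90 values or on changes. Both are legitimate, but they differ in power and react in opposite directions to a chance baseline difference. If the choice is not fixed in advance, it can be made after the data are seen.

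Second, the pre/post tests stand level with the between-arm tests. A pre/post test cannot separate the product's effect from change that would also occur on placebo, such as regression to the mean or the course of disease on 5-ASA. A report that the Ganoderma arm improved significantly and the placebo arm did not could be read as efficacy when the arms do not differ.

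The point concerns numeric outcomes. The between-arm categorical test (item c) and biopsy are outside it. Item e enters only because it is a pre/post test with the same decision threshold.

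**Working it through.** **Inputs.** The protocol gives 92.25 per group before drop-out; 92.25 × 1.10 = 101.5, rounded up to its 102. I use n = 92 evaluable per arm and two-sided α = 0.05. How 92.25 itself was obtained is a separate matter. The documents give no SD, effect size or correlation for any numeric outcome. The following are therefore assumptions: equal SDs at both visits, baseline/day-90 correlation r = 0.3, 0.5 or 0.7, and a between-arm effect d = 0.40 day-90 SDs.

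**1. Separate pre/post tests, no treatment effect.** I read item d as applied within each arm. Both arms shift by δ, in SDs of the change. Each arm's paired t-test (91 df, noncentrality δ√92) is significant with probability p. The active arm alone is significant with probability p(1 − p).

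| δ | p | p(1 − p) |
|---|---|---|
| 0.1 | 0.158 | 0.133 |
| 0.2 | 0.475 | 0.249 |
| 0.3 | 0.812 | 0.152 |
| 0.5 | 0.997 | 0.003 |

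The maximum possible value is 0.25, at p = 0.5. A between-arm test rejects in 5% of such trials, counting both directions.

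**2. Between-arm power at d = 0.40.** In units of the day-90 variance, the analysed variance is 1 for day-90 values, 2(1 − r) for changes and 1 − r² for ANCOVA. The noncentrality is 0.40 × √(92/2) ÷ √variance, with 182 df (181 for ANCOVA).

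| r | Day-90 t-test | Change t-test | ANCOVA |
|---|---|---|---|
| 0.3 | 77.0% | 62.6% | 80.8% |
| 0.5 | 77.0% | 77.0% | 87.6% |
| 0.7 | 77.0% | 93.6% | 96.6% |

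Which unadjusted test is better depends on r, which is not known in advance. ANCOVA is highest in every row.

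**3. Mann-Whitney branch.** In a simulation of 10,000 trials with a log-normal marker (log-SD 1, shift 0.40 log-SD), power for r = 0.3, 0.5 and 0.7 was:

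- day-90 values: 76%, 75%, 75%
- raw changes: 59%, 73%, 91%

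Log-scale ANCOVA has the power in the ANCOVA column above (81%, 88%, 97%), because the log data are exactly normal here. That favours it somewhat.

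**4. Chance baseline imbalance.** The SE of the baseline difference is √(2/92) = 0.147 SD, so a difference above 0.3 SD in either direction has probability 0.042 per outcome. Given a difference of exactly 0.3 SD and no effect, the expected shift is +0.3r for day-90 values and −0.3(1 − r) for changes. With conditional variance proportional to 1 − r² (normal approximation), the false-positive rates are:

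| r | Day-90 values | Changes | ANCOVA |
|---|---|---|---|
| 0.3 | 8.2% | 17.4% | 5% |
| 0.5 | 13.8% | 13.8% | 5% |
| 0.7 | 22.7% | 10.3% | 5% |

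**5. Choosing the test afterwards.** In 20,000 simulated null trials with normal data, the day-90 and change t-tests each rejected at about 5%. At least one of the two rejected in 9.2%, 8.8% and 9.2% of trials at r = 0.3, 0.5 and 0.7.

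**The case against.** The unadjusted comparison is valid because the trial is randomised, and averaged over all randomisations each candidate test holds its 5%. ANCOVA is thus a gain in efficiency, not a repair of an invalid test. Over the better unadjusted test the gain can be small: about 4 points over day-90 values at r = 0.3, and about 3 points over changes at r = 0.7. The imbalance rates are conditional on an event seen in 4% of trials per outcome. All of this stands, and it limits the severity.

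The documents also lean one way on the quantity. The specific objectives speak of outcomes after administration and no passage mentions a change score, so comparing levels is the natural reading of item b. This narrows the ambiguity without removing it: item b names no visit, and Study Design frames the analysis as pre and post.

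No passage says efficacy will be judged from items d or e, and the between-arm items come first. The 25% is the worst case over the assumed shift. Item d also does not state that it is applied within each arm, although a pooled pre/post test would say even less about treatment. These are fair limits, but no sentence rules out the misreading, and one sentence would.

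Finally, the sample size is built on an unnamed proportion. A numeric ANCOVA therefore cannot serve as the trial's primary analysis until a primary outcome is named. That too is right, and the recommendation is confined to numeric outcomes.

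**Conclusion.** The concern holds, as something the sponsor should change rather than a fatal flaw. Three facts are plain from the text: item b does not define what is compared, no item adjusts for baseline, and the pre/post tests share the between-arm tests' threshold with no ranking.

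The consequences are a possible active-only significance of up to about 25% with no treatment effect, a power spread of roughly 14 to 17 points between the two readings of item b at r = 0.3 or 0.7, and near-doubling of the per-outcome type I error if the reading is picked after the data are seen. These sizes depend on the assumed correlations, shifts and effect. The ordering, with ANCOVA at least as powerful as either unadjusted test, holds at every correlation examined.

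**What to change.** In Data analysis:

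1. For each numeric outcome (including the Mayo score if it is analysed as a number), make the between-arm analysis an ANCOVA of the day-90 value on arm, with the baseline value as covariate.
2. Fix in advance, marker by marker, whether a log scale is used, applying it to markers expected to be skewed. Report the adjusted difference, or ratio on the log scale, with a 95% confidence interval.
3. State in item b that the t-test or Mann-Whitney test compares day-90 values, and keep it as a sensitivity analysis.
4. State that items d and e are descriptive and that efficacy is concluded only from the between-arm comparison.

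The cost is SAP wording and slightly more analysis work. No new data and no extra patients are needed.
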